Note: No IND was sought to enroll children into the trial with the apo-varenicline study medication, as it was being used under temporary FDA authorization. When US-made, generic varenicline was FDA approved (August 2021) and available for purchase through PAR Pharmaceuticals (November 2021), an IND was sought (December 2021) to enroll children ages 16 and 17 into the trial. This trial was deemed exempt in March 2022. When IND exemption was granted for enrolling children ages 16 and 17, IRB approval was sought for the main trial which will uses generic US made varenicline in participants ages 16-25.

III. SUBJECT SELECTION

a. Inclusion/exclusion criteria

Inclusion Criteria:

- Ages 16-25, inclusive;
- Self-report of daily or near daily nicotine vaping for the prior \geq 3 months and semiquantitative saliva screening for cotinine positive for recent nicotine use;
- Nicotine dependence as defined by a score ≥4 on the 10-item E-cigarette Dependence Inventory (ECDI), or report of persistent use despite negative consequences, or prior failed quit attempts;

- Self-report of no regular combusted tobacco use in the past 2 months at enrollment and exhaled CO <10 ppm;
- Total body weight at enrollment \geq 35 kg (77 lbs);
- Report willingness to try varenicline to stop vaping;
- Able to understand study procedures and read and write in English;
- Have a parent or legal guardian who is able and willing to provide written informed consent (if under the age of 18);
- Competent and willing to provide written informed consent (if age 18+) or assent (if under 18);
- For participants who could become pregnant: negative urine pregnancy test at enrollment and agreement to use effective contraception (e.g., abstinence, hormonal contraception, intra-uterine device, sterilization, or double barrier contraception) during the study.

Exclusion Criteria:

- Use of a smoking cessation medication in the prior month (nicotine patch, gum, nasal spray, or inhaler, varenicline, bupropion);
- Unwilling to abstain during the study from using smoking cessation aids other than those provided by the study;
- Unstable medical condition, epilepsy, severe renal impairment;
- Inpatient psychiatric hospitalization in the prior 6 months, serious suicidal ideation or suicide attempt within 6 months of enrollment, recent active suicidal ideation or suicidal behavior identified at enrollment or baseline visits;

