b. Procedures for obtaining informed consent Waived Parental Consent for Phone Screening Only (for participants under age 18): We request a waiver of parental consent for those under age 18 for phone screening only, which is justified given the following: The proposed phone screening involves no more than minimal risk to participants. During the phone screening, we will provide details about the study and ask potential participants if they have any questions or concerns about the study protocol. We will also ask participants basic demographic information as well as brief questions related to symptoms of psychopathology to assess eligibility. They will be told that all information will be kept strictly confidential and answers to screening questions will be stored separately from any identifying information. Participants are free to refuse to answer any questions. Participants will also have the option to complete the initial screening via a REDCap survey that will be accessible through the study's approved Massachusetts General Hospital Rally page. If participants are interested in the study and are eligible, we will collect parents/guardian's contact information so that we can obtain written parental consent for study enrollment. No study procedures will occur before written parental consent is obtained. We will also obtain written assent from the participant prior to the initiation of any study procedures.

The waiver of consent for phone screening will not adversely affect the rights and welfare of subjects. The waiver of parental consent for screening only will not adversely impact an adolescent's access to or the nature of any ongoing health services or primary care in any way nor adversely affect his/her rights or welfare. The study will be explained in detail to potential participants before any screening questions are asked, giving them a chance to decline screening if they are not interested in the study. They are also free to refuse to answer any screening questions that make them feel uncomfortable. They will be clearly told that written parental consent and adolescent assent will be required for enrollment in the active study phase and that answers to phone-based questions are for screening purposes only.

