Limits of Confidentiality on Clinical Information (Emergency Protocol): While we are committed to maintaining confidentiality to the extent to which we are able, confidentiality is limited when there is a deemed imminent risk to oneself or others or reports of child and elder abuse. Study staff will inform participants during the consent process that in emergency situations (in which an individual is at immediate risk for harm) we will release information about the participant. Specifically, if a participant tells any member of study staff that they have intent and/or a plan to cause harm to self or others, study staff will start the Center Emergency protocol that includes a psychiatric evaluation by a licensed mental health professional and even calling 911. If the participant says that they have recurrent thoughts about harming themselves or someone else but does not have intent or plan to do so, study staff will ask participant permission to notify appropriate medical or counseling personnel, including the guidance counselor or therapist. If study staff learns about mood concerns or problematic substance use, study staff will provide the participant with referral resources for follow-up consultation and care. The PI has prepared a comprehensive list of local and national resources for this purpose.

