For participants under age 18: Parents and staff members at participating schools, will not be provided any information regarding study participants, including substance use habits, unless there is imminent risk of harm to self or others in the opinion of the PIs. In the consent/assent forms, both parents and participants are informed that only in emergency situations (in which an individual is at imminent risk of harm) would we release any information. Specifically, if a participant tells us that he/she has intent and/or a plan to cause harm self or other, we will tell the parents, and call 911. If the participant says that he/she has recurrent thoughts about harming him/herself or someone else but does not have intent or a plan to do so, we may notify parents and other appropriate medical or counseling personnel if clinically indicated in the opinion of the PIs. Finally, if a participant discusses details about ongoing child abuse, we will report such abuse to the Department of Child and Families directly. If we learn about mood concerns or problem substance use, we will provide the participant with local and trusted resources for follow-up consultation and we will ask him/her if this information can be disclosed to his/her parents to help coordinate and facilitate care.

Confidentiality of Drug Tests: The results of the qualitative and quantitative drug testing will be confidential. The only individuals who will have knowledge of the results of these tests are research staff directly working on the project. Information will be stored in a secure computer database that uses participant codes (rather than names) as identifiers.

v. Randomization in Clinical Trials Risk: Participants will be assigned to an intervention by chance, using computer generated random allocation code produced by the MGH Research

Pharmacy. The study arm to which a participant is assigned may prove to be less effective than an alternate study arm.

VIII. POTENTIAL BENEFITS

a. Potential benefits to participating individuals

The study will potentially help individuals to stop vaping or substantially reduce their exposure to vaporized nicotine.

b. Potential benefits to society

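### Minors are promised unqualified confidentiality at the pre-consent screen, while the protocol's own limits on confidentiality are explained only at consent, which a screened-out minor never reaches

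*Combined protocol and SAP*

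**What the plan says.** **At the screen.** Under Waived Parental Consent for Phone Screening Only (Section IV.b), the plan states: "We request a waiver of parental consent for those under age 18 for" the phone screen. The screen contains "brief questions related to symptoms of psychopathology to assess eligibility", and a REDCap survey may replace the call. On confidentiality the minors get one message: "They will be told that all information will be kept strictly confidential". The section adds that answers are stored apart from identifiers. It states no exception for risk of harm or for abuse.

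**Parent contact.** The same section says: "If participants are interested in the study and are eligible, we will collect parents/guardian's contact information". Written Parental Consent for Study Enrollment, also in IV.b, repeats the condition: the minor must be interested and likely eligible on the screener.

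**Limits of confidentiality.** Section VII.iv (Limits of Confidentiality on Clinical Information) says that confidentiality is limited for imminent risk and for reports of abuse. The trigger is a disclosure made to any member of study staff. On timing it says: "Study staff will inform participants during the consent process that in emergency situations" information will be released. The paragraph for participants under 18 says that, where a minor states intent or a plan to harm, "we will tell the parents, and call 911". It adds that ongoing child abuse is reported to the state agency. It says that parents and participants learn of the emergency exception through the consent/assent forms.

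**Eligibility.** Section III.a excludes, among others, those with "serious suicidal ideation or suicide attempt within 6 months of enrollment".

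**The concern.** The confidentiality promise comes before the psychopathology questions are answered and before anyone has consented or assented. The exceptions to it come later, in a process that only minors who pass the screen enter. A minor who is screened out has heard the promise and not the exceptions.

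At stake is how 16- and 17-year-olds are treated at first contact. If one of them discloses intent to harm during the screen, acting on Section VII.iv would break what the minor was told. If that minor is also ineligible, no written step gives staff a parent to tell.

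The waiver request in Section IV.b is also involved. It rests on minimal risk, minimal privacy risk, and no adverse effect on minors' rights and welfare. A promise that the protocol's own rule may require staff to break weakens that basis.

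**Working it through.** No arithmetic applies. The check sets the passages side by side and follows one minor through the documented sequence.

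| Step | What the plan provides | Where |
|---|---|---|
| 1 | Parental consent waived for the screen; written consent and assent come later | IV.b, Waived Parental Consent |
| 2 | Minor is told all information is confidential, with no exception | same |
| 3 | Psychopathology questions asked, by phone or REDCap | same |
| 4 | Suppose the minor discloses intent or a plan to do harm | trigger in VII.iv |
| 5 | If the minor is found ineligible, no parent contact is collected | IV.b, both parental-consent paragraphs |
| 6 | Staff are to tell the parents and call 911; in general, start the emergency protocol with psychiatric evaluation | VII.iv |
| 7 | Limits of confidentiality explained | consent process and forms (VII.iv), not reached |

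**Promise against rule.** Step 2 admits no exception and step 6 is one. Step 7 would cure the mismatch only if it came before step 2; it comes after. The Certificate of Confidentiality paragraph in Section VII.iii also carries exceptions for abuse and for harm to self or others. Of these statements, only the one used at the screen is unqualified.

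**Rule against means.** Step 6 contains several actions. The 911 call, the psychiatric evaluation and the child-abuse report need no parent contact details. Only parent notification does, and step 5 leaves it without a written source. In the school stream, the form described in Section IV.a collects the student's contact information, not a parent's.

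**Does Section VII.iv apply at the screen?** The documents do not say so expressly. Two features favour it: Section IV.b calls screened minors participants, and the trigger is disclosure to any staff member. One feature points the other way: the explanation of limits is tied to consent. If the section applies, the promise contradicts the rule. If it does not, the sections reviewed give no emergency rule for a contact that asks minors about psychopathology. Either way the passages need reconciling.

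**Who is reached.** Section IV.a restricts research invitations to adults, so minors enter through school screening and through self-referral or referral by others. The number of minors screened is not stated. The figure of up to 300 in Section II refers to enrollment at all ages, so it does not supply that number.

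**The case against.** The strongest reply is that the emergency text was written for enrolled participants, that staff on a live call can ask for a parent's number or call 911, and that the safety SOP cited in Section VII.i may cover screening. Part of this stands. Nothing forbids staff from asking, most emergency actions are unaffected, and neither the SOP nor the screening script is available to check. But asking is not a written step, and it is not available in the same way when answers are entered in REDCap. An SOP on staff conduct also would not change what the protocol says minors are told.

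A reader might infer more than the documents support:

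- *That the screen is aimed at suicidality.* No passage says it asks about it. Section VII.i also lists schizophrenia and bipolar disorder as exclusions, and the C-SSRS is given at enrollment (Section V.f). A disclosure at the screen may simply be volunteered.
- *That a minor excluded for suicidality is one who triggers the emergency rule.* The exclusion concerns ideation or an attempt within 6 months; the rule requires stated intent or a plan. For recurrent thoughts without either, Section VII.iv says only that parents may be notified. The two groups overlap but are not the same.
- *That staff could not act, or that parents could not be told.* Only the written means for one step is missing.
- *That every recruitment route is affected.* Research invitations go to adults only.

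It is also fair to object to taking parent details from every minor at the outset. Section IV.b justifies the waiver partly by limiting collection to basic demographics and eligibility information, so early collection would cut against that justification.

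**Conclusion.** Wrong as written: an internal contradiction between Section IV.b and Section VII.iv. The unqualified promise applies to every under-18 who is screened. The gap in parent notification is narrower. It concerns minors from whom no parent contact is taken, chiefly those found ineligible, and it matters only when the emergency rule is triggered. The documents give no basis for estimating how many that would be.

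Calling it a contradiction assumes that Section VII.iv reaches people who are only being screened, which its wording supports but does not state. If it does not, the defect is an absent rule for screening, and the same passages need attention. The unseen SOP or script might already deal with part of this.

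This is a matter of consent and participant protection. It has no bearing on endpoints, power or analysis.

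**What to change.** Reconcile the screening and parental-consent paragraphs of Section IV.b with Section VII.iv:

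1. State whether the limits of confidentiality apply from first screening contact, including answers entered in REDCap.
2. Replace the unqualified promise in the phone script and the REDCap screener with wording that matches that decision, placed before the psychopathology questions.

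Two matters are for the investigators and the IRB: which disclosure rule governs, and whether and when parent contact is needed for screened minors, given the minimal-data argument in the waiver request.

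The cost is edits to the protocol, script and screener, and an IRB amendment. The screen becomes slightly longer, and some minors may disclose somewhat less once they hear the limits.

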Eligible participants will be randomly assigned in a 1:1:1 ratio, in blocks of 6, to varenicline, identical appearing placebo prepared by the MGH research pharmacy, or EUC (i.e., TIQ and monitoring with assessments only). Study staff and participants will both be blind to drug for those randomized to the varenicline and placebo arms. Randomization will be stratified by secondary or post-secondary school status. The randomization scheme will be computer generated by the MGH Research Pharmacy by personnel with no other interactions with study staff or participants. There will be separate randomization codes for apo-varenicline, imported from Canada under a provisional FDA allowance, and domestic generic varenicline with full FDA approval. The randomization codes will be held in the MGH research pharmacy, and available to study PIs only in the case of urgent medical need. Assessments will be conducted by study staff who are blind to study intervention. Treatment will be assigned according to study

number, assigned sequentially to eligible participants who enroll in the trial and attend the baseline visit.

Special considerations for individuals living in the same households: More than one household member or family member will be allowed to participate in the study. Since there is a possibility that participants from the same household, voluntarily or not, share study medication, participants from the same household will be yoke randomized, eg assigned to the same intervention. Yoked randomization will ensure members of the same household or family members receive the same intervention and will reduce the risk for contamination.

V. STUDY PROCEDURES

Participants will be randomly assigned to receive a 12-week course of varenicline, an identical placebo, or EUC only. Participants assigned to receive varenicline or identical placebo will receive individual behavioral vaping cessation sessions (held virtually by videoconferencing or in-person), and a digital platform to report vaping behavior, study medication adherence, and tolerability. Participants in EUC will be provided with explicit advice to quit and non-directive support. Participants in all three arms will complete assessments, conducted by raters blinded to study arm assignment, and will include samples for cotinine assays and self-reports of vaping and other drug use. Participants in all three arms will receive an introduction to TIQ and receive weekly monitoring of TIQ use from study staff.

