Before behavioral intervention sessions, participants will fill out assessments of vaping craving and collect saliva for cotinine testing (the latter only occurring if the participant self-reports nicotine abstinence since the last weekly visit). To refine and tailor these interventions to be maximally appealing to and effective for adolescents who vape, we will ask participants for weekly feedback on the appeal, relevance, and effectiveness of the educational topics and skills covered in the program. For participants randomized to the EUC arm, weekly sessions will only consist of non-directive support and assessments noted in the Time and Events Table, including saliva samples for cotinine (collected only to bio-verify self-reported nicotine abstinence).

| Time | Activities |
|--------|---|
| 5 mins | Check-in on adverse events, vaping exposure, and medication adherence |
| 3 mins | New educational content |
| 7 mins | Review of education material and skill/behavior goal |

CBT Structure

Prior to initiating the study intervention, interventionists will complete training conducted by [name] or other doctoral members of study staff on QuitVaping sessions. This will include didactic training on vaping and vaping cessation in adolescents, study methods, theoretical rationale, and background information on the behavioral and pharmacologic interventions. At the end of the training, leaders must achieve a minimum score of 80% on the fidelity scale based on their facilitation of two simulated sessions before they lead a session.

e. Enhanced Usual Care (EUC)

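### A single published block size of 6 with a visible EUC arm lets staff who track allocations foresee EUC or not-EUC status for up to 28.9% of participants; withheld, varying block sizes are a cheap improvement

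*Combined protocol and SAP*

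**What the plan says.** Section IV.c (Treatment assignment, and randomization) sets the scheme: "Eligible participants will be randomly assigned in a 1:1:1 ratio, in blocks of 6". It adds: "Randomization will be stratified by secondary or post-secondary school status". Treatment follows the study number, which is "assigned sequentially to eligible participants who enroll in the trial and attend the baseline visit". Nothing says that the block size varies or is kept from enrolling staff.

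Three safeguards are stated in the same section:
- Blinding: "Study staff and participants will both be blind to drug for those randomized to the varenicline and placebo arms".
- Custody of the list: "The randomization codes will be held in the MGH research pharmacy, and available to study PIs only in the case of urgent medical need". It is generated by pharmacy personnel who have no other contact with study staff or participants.
- Outcome assessment: "Assessments will be conducted by study staff who are blind to study intervention".

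The blinding statement covers varenicline against placebo only. The EUC arm differs openly in content. Section V.d says: "For participants randomized to the EUC arm, weekly sessions will only consist of non-directive support and assessments". Section V.a dispenses medication at baseline only to the other two arms, and the payment schedule differs for EUC.

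**The concern.** Keeping the list in the pharmacy hides future entries, but it does not stop staff working them out from arms already revealed. Once both EUC places in a block are used, or all four non-EUC places, the status of every remaining place in that block is settled. The block size is printed in the protocol, and a candidate's stratum is known before allocation.

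There is a route by which such knowledge could act. Section V.a separates the enrollment visit from the baseline visit, so staff schedule baseline after eligibility has been assessed. Willingness and motivation to quit are recorded at enrollment (Section V.f), and eligibility includes criteria left to the investigator's opinion (Section III). Staff could, knowingly or not, bring more or less promising candidates forward when the next status is foreseeable. Either kind of certainty can do this, EUC or not-EUC.

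At stake are the comparisons with EUC. These include Hypotheses 1.4 and 1.6, the only Aim 1 secondary tests of whether the behavioral sessions given with placebo improve on EUC.

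**Working it through.** The documents give no predictability figure, so there is nothing to reproduce first.

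**Inputs.** Block size 6 and ratio 1:1:1 (Section IV.c) give 2 EUC and 4 non-EUC places per block. Up to 240 participants are randomized (Section II). I take the block size as constant because no variation is mentioned. The observer knows the block size and logs every allocation by stratum.

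**Certainty under blocks of 6.** There are C(6,2) = 15 equally likely orderings. A position is certain if all places from it to the end of the block are of one type.

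| Position | Certain EUC | Certain not-EUC | Either |
|---|---|---|---|
| 1 | 0 | 0 | 0 |
| 2 | 0 | 0 | 0 |
| 3 | 0 | 1/15 | 1/15 |
| 4 | 0 | 3/15 | 3/15 |
| 5 | 1/15 | 6/15 | 7/15 |
| 6 | 5/15 | 10/15 | 15/15 |
| Sum | 6/15 | 20/15 | 26/15 |

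Dividing by 6 positions:
- either status: 26/90 = 28.9%, about 69 of 240
- certain EUC: 6/90 = 6.7%, about 16 of 240
- certain not-EUC: 20/90 = 22.2%, about 53 of 240

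Stratification leaves these shares unchanged, because each stratum is blocked separately and the stratum is known.

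**Best guess under blocks of 6.** At each position the observer names the type with more places left. The expected accuracies at positions 1 to 6 are 10/15, 10/15, 10/15, 11/15, 11/15 and 15/15. Their sum is 67/15, and 67/90 = 74.4%. Always guessing not-EUC gives 4/6 = 66.7%.

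**One unseen allocation.** If one allocation in the same stratum goes unseen, each position is judged on the information available one place earlier. The sum becomes (0 + 0 + 1 + 3 + 7)/15 = 11/15, and 11/90 = 12.2%.

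**Varying block sizes.** I simulated lists of 120 per stratum. The observer knows the set of possible sizes but not the current one, and updates by Bayes' rule. The size sets are illustrative assumptions.

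| Sizes | Certain status | Best-guess accuracy |
|---|---|---|
| 6 only | 28.9% | 74.4% |
| 3, 6 | about 10% | about 75.5% |
| 3, 6, 9 | about 4% | about 73.7% |
| 6, 9, 12 | about 2% | about 71.8% |

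**Tests exposed.** The Aim 1 secondary efficacy tests are H1.1 at weeks 9-24 (1), H1.2 (1), H1.3 (2), H1.4 (2), H1.5 (1) and H1.6 (1), which makes 8. H1.3 to H1.6 use EUC: 2 + 2 + 1 + 1 = 6.

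**The case against.** **The figure is a ceiling.** It needs someone who records every allocation by stratum and acts before the next one in that stratum. The documents do not say that those who book baseline visits know the position in the block, and one unseen allocation cuts the certain share to 12.2%. This stands, and the figure should be read as an upper bound. Against it, one team runs the trial, and investigators and coordinators meet weekly (Section IX.d), so past allocations could be pooled.

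**Most of the certainty is of not-EUC.** A reader might take 28.9% as how often staff know that EUC comes next. That is true for only 6.7%. In the other 22.2% they know it is not EUC but cannot tell varenicline from placebo. The split must be shown, although steering candidates toward known non-EUC places would distort the same contrasts.

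**Other safeguards exist.** Blinded raters protect the assessment of outcomes, not the decision on who enters when. The models in Section VI adjust for sex, school environment and dependence severity, which gives partial protection. Motivation is not a covariate, but it is measured before randomization, so imbalance in it could be examined. Selection on unmeasured traits would remain.

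**Varying blocks may gain little.** This is correct if blocks of 3 are included. Sizes 3, 6 and 9 cut certainty to about 4% but leave best-guess accuracy almost unchanged, and sizes 3 and 6 make it slightly worse. Selection does not require certainty, so the choice of sizes matters.

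**Conclusion.** The point holds as a vulnerability that is cheap to reduce. Up to 28.9% of allocations could be foreseen with certainty as EUC or not-EUC, and an ideal observer's best guess gains 74.4 - 66.7 = 7.7 percentage points over always guessing not-EUC. Six of the eight Aim 1 secondary efficacy tests could be affected.

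Two stronger conclusions are tempting but not supported. The documents do not show that the EUC contrasts are biased: nothing says that staff count allocations or act on them, and no effect on abstinence rates can be derived. Nor is the primary varenicline-placebo contrast exposed by this route, because staff cannot tell those two arms apart.

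The result rests on a constant block size, which is inferred from the wording, and on full tracking within strata. The calculation leaves out yoked household members. Their arm is known in advance and they may disturb the counting of blocks, but their number is not given. The count of six of eight covers Aim 1 only. In Aim 2, the EUC contrasts under Hypothesis 2.1 are exploratory.

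**What to change.** In Section IV.c, replace the stated block size with permuted blocks of randomly varying size within the school strata, generated by the research pharmacy. Avoid blocks of 3; sizes 6, 9 and 12 are one workable set. Keep the sizes in a document held by the pharmacy, withheld from study staff and removed from the protocol. Apply this to all allocations still to be made. It cannot help those already made, and the documents do not say how many remain.

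The pharmacy regenerates the remaining list and one sentence of the protocol changes. The ratio, strata, sample size and analysis stay as they are. The downside is slightly more possible imbalance between arms if the last block in a stratum is incomplete.
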